**For subjects receiving rivaroxaban who enroll in the extension, the last dose will be the EoT visit date -1 day.**

### 2.3. Clarification on major bleeding type in section 6.6.1 of the SAP

The primary endpoint variable is defined as time to first event of composite of ISTH-defined major bleeding (**including non-intracranial events and the following cerebrovascular events: Hemorrhagic Stroke, Ischemic Stroke with Hemorrhagic Transformation, Other Intracranial/Intraspinal Hemorrhage**) or CRNM bleeding events occurring from randomization through EoT date.

### 2.4. Change in the Intent-to-Treat (ITT) in section 3.4 of the SAP

The ITT will consist of all patients randomized and ~~does~~ it is to be analyzed according to randomized treatment assignment.

Please note that this is also a change from section 10.1 of the protocol.

### 2.5. Definition of the Per Protocol Population

All randomized patients with a treatment compliance rate of at least 80% **that** do not have any major protocol violations **as defined following clinical review prior to database lock**.

### 2.6. Additional Exploratory Endpoints

The following exploratory endpoints are added:

- Time to first event of composite of International Society on Thrombosis and Haemostasis (ISTH)-defined major bleeding or CRNM or minor bleeding events
- Total number of International Society on Thrombosis and Haemostasis (ISTH)-defined major bleeding or CRNM or minor bleeding events
- Total number of International Society on Thrombosis and Haemostasis (ISTH)-defined major bleeding events
- Total number of International Society on Thrombosis and Haemostasis (ISTH)-defined CRNM bleeding events
- Total number of International Society on Thrombosis and Haemostasis (ISTH)-defined minor bleeding events

The time to event endpoint will be analyzed following the procedures outlined in Section 6.6.1 of the SAP. The total number of events endpoints will be analyzed following the procedures outlined in Section 6.6.4.1 of the SAP. The number and percentage of patients with at least one ISTH-defined major bleeding or CRNM or minor bleeding events will also be presented respectively.

### 2.7. Subgroup Analyses of Primary Endpoint

Subgroup analyses of primary endpoint will be performed for the following subgroups:

- Geography
  - North America
  - Outside North America

## TITLE: Statistical Analysis Plan Addendum Template

- Race
  - White
  - Non-white
- Age (Years)
  - < 65
  - 65-79
  - >= 80
- Sex
  - Male
  - Female
- Weight
  - <= 60 kg
  - > 60 kg
- Creatinine Clearance
  - <= 50 min/mL
  - > 50 min/mL
- Baseline antiplatelet use
  - Yes
  - No

Subgroup analyses will be analyzed following the procedures outlined in Section 6.6.1 of the SAP with the exception that the stratification factors are not included as adjusting factors. A forest plot of the hazard ratios and 95% CI from subgroup analyses will be presented. No adjustments will be made for multiple testing.

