## 3.2 Rationale for study design

The primary objective of this study is to evaluate the bleeding profile of abelacimab relative to rivaroxaban in patients with AF at moderate-to-high risk of stroke.

Rationale and justification for the key elements of the study design are as follows:

[figure not shown]
- **Randomization:** This decreases the chance of an imbalance in patient characteristics between treatment groups.
- **Stratification:** Randomized patients will be stratified into treatment groups according to their concomitant use of antiplatelet medications at baseline and renal function since these factors may influence the underlying bleeding risk in patients.
- **Blinding:** The study will be open-label with respect to abelacimab vs. rivaroxaban; however, investigators and patients randomized to abelacimab will be blinded to the abelacimab dose. This design allows more simplicity in the conduct of the trial and decreases the patient's burden by eliminating the need to receive placebo injections of the study drug in patients randomized to rivaroxaban or the need to take a daily placebo in patients randomized to abelacimab.  
Bias will be avoided by following strict randomization procedures and having study endpoints adjudicated by an independent CEC comprised of qualified experts who will adjudicate events in accordance with endpoint evaluation guidelines.
- **Active control:** Provides a comparison group for safety, tolerability, and efficacy endpoints.

The patient population will be described in more detail in [Section 4](#) below.

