## 6.2 Treatment assignment and randomization

Patients will be randomized on Day 1 to one of the following treatment arms in a 1:1:1 ratio:

- Abelacimab (MAA868) 90 mg s.c. monthly
- Abelacimab (MAA868) 150 mg s.c. monthly
- Rivaroxaban 20 mg p.o. once per day with evening meal

[Note: Patients with a CrCl  $\leq$  50 ml/min by the Cockcroft-Gault equation will have a dose adaptation to rivaroxaban 15 mg p.o. daily.]

Randomization into treatment groups will be stratified by the use of concomitant antiplatelet use at baseline (yes/no) and renal function (CrCl  $\leq$  50 ml/min or CrCl  $>$  50 ml/min). Patients randomized to the rivaroxaban arm may be dose adjusted between the 15 mg dose and 20 mg doses depending on CrCl values.

Once a subject is stratified and randomized, the subject will stay in that starting stratum, randomized treatment group, and treatment regimen for analyses purposes even if their dose is subsequently adjusted.

Once Investigators have ascertained that the patient is eligible for the study, they will contact the Interactive Web or Voice Response System (IxRS) before the first administration of study drug. The IxRS will require the following information in order to randomize a patient to the correct stratification: year of birth, CrCl (Cockcroft-Gault) and whether the patient takes antiplatelet medications (i.e., aspirin and/or a P2Y12 inhibitor) as a concomitant medication. The IxRS will allocate the treatment group assignment for the patient.

Emergency unblinding will be done through the IxRS system. The treatment code should not be broken except in medical emergencies when the appropriate management of the patient requires knowledge of the treatment assignment. The decision of whether or not to unblind lies with the investigator and it is the sole responsibility of the investigator to determine the need for immediate unblinding. However, if time and circumstances permit, the Investigator is encouraged to contact the [REDACTED]  
[REDACTED]  
[REDACTED]

The specifications for generation of the randomization schedule will be prepared by the study biostatistician and the contract research organization (CRO) in charge of the IxRS. An independent biostatistician, not otherwise part of the clinical study execution team, will generate the randomization schedule. The randomization numbers will be generated to ensure that treatment assignment is unbiased.

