### 2.2.3. Exploratory Objectives

### 2.3. Sample Size and Power

The primary endpoint is the composite of major or CNRM bleeding. The study is event driven. At the start of trial it was assumed a HR of 0.60 for each dose of abelacimab compared with rivaroxaban, thereby, a total of at least 166 events would provide at least 80% power for each abelacimab arm vs. rivaroxaban with a 2-sided alpha of 0.05. Given an expected 15% per year event rate in the rivaroxaban arm, a 10% annual dropout rate (death, withdrawal of consent,

lost-to-follow-up), approximately 1,200 patients would provide the requisite number of events over an approximate total trial duration of 27 months.

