## 6.6. Primary Analysis

### 6.6.1. Primary Analysis

The primary endpoint variable is defined as time to first event of composite of ISTH-defined major bleeding or CRNM bleeding events occurring from randomization through EoT date. Patients alive and on-study without an event will be censored at the EoT date. Patients lost to follow-up or who otherwise discontinued study follow-up prematurely without experiencing any event will be censored at the EoT date, as defined in Section 3.1. Patients who did not experience any event before death will be censored at the earlier of the date of death and EoT date.

The primary analysis will compare each abelacimab regimen with rivaroxaban for the time from randomization to first occurrence of major or CRNM bleeding in the On-Treatment Analysis Set. For each treatment regimen, the event rates at 6-month intervals will be estimated with 95% confidence intervals (CIs). For each comparison, the time to first event will be tested using the stratified log-rank test and the treatment effect estimated using the Cox proportional hazards model including treatment and the following two stratification factors as covariates:

- Planned use of concomitant antiplatelet medication use (e.g. aspirin and/or P2Y12 inhibitor) for the duration of the trial
- CrCl (Cockcroft-Gault)  $\leq 50$  ml/min

The hazard ratios with 95% CIs and two-sided p-values will be reported for both doses of abelacimab vs. rivaroxaban. A significance level of  $\alpha=0.05$ , without adjustment for multiplicative testing, will be used.

An inverted Kaplan-Meier plot will be drawn and estimates of the event rate at 6-month intervals will be presented.

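### The subgroup analyses added after database lock specify no treatment-by-subgroup interaction, so the separate within-level results cannot show whether the effect differs

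*SAP*

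**What the plan says.** SAP 6.6.1 compares each dose with rivaroxaban by a stratified log-rank test and estimates the effect from "the Cox proportional hazards model including treatment and the following two stratification factors as covariates". The factors are antiplatelet use and creatinine clearance at or below 50 ml/min. Protocol 3.2 explains the stratification: "since these factors may influence the underlying bleeding risk in patients". For each dose, 6.6.1 reports a hazard ratio, a 95% CI and a two-sided p-value at the 0.05 level.

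Addendum 2.7 adds subgroup analyses of the primary endpoint by geography, race, age, sex, weight, creatinine clearance and baseline antiplatelet use. Age has three levels and the other six factors have two, so there are 15 levels and, with two doses, 30 hazard ratios. They follow 6.6.1 "with the exception that the stratification factors are not included as adjusting factors". The addendum does not say whether the log-rank test also becomes unstratified. The only output it names is a forest plot of hazard ratios with CIs, and it states that multiplicity is not adjusted for. It names no interaction term, interaction p-value or rule of interpretation, and none appears elsewhere in the visible protocol or SAP. Addendum 1 places these changes after the lock of 08Mar2024.

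**The concern.** A subgroup forest plot raises the question of whether the treatment effect differs between levels. A hazard ratio, CI and p-value computed separately in each level do not answer it. A trial sized for one overall comparison has too few events in most subgroups, so one level will often be significant and the other not when the effect is identical in both. That pattern is easily read as effect modification, for example as a bleeding advantage confined to one region or to patients with better renal function.

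The timing adds to this. The subgroups were specified after lock, in a trial that is open-label between abelacimab and rivaroxaban, and Addendum 2.7 does not itself call them post hoc or exploratory. No primary or secondary objective depends on them. What is at stake is how the subgroup results are read.

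**Working it through.** **Inputs.** From SAP 2.3: "it was assumed a HR of 0.60 for each dose of abelacimab compared with rivaroxaban"; "at least 166 events would provide at least 80% power for each abelacimab arm vs. rivaroxaban"; "with a 2-sided alpha of 0.05"; and "Given an expected 15% per year event rate in the rivaroxaban arm". Allocation is 1:1:1 (Protocol 6.2). Protocol 1.2.2 gives the shares: creatinine clearance at or below 50, about 20%; antiplatelet use, about 24%; North America, 335/1287 = 26%; female, 44%. Splitting events in proportion to these shares is an assumption.

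**Step 1: reproduce the plan's figure.** Pairwise events needed (Schoenfeld) = 4 × (1.960 + 0.842)² / (ln 0.60)² = 120.3. Scaled to three arms by expected event share: 120.3 × (1 + 0.6 + 0.6)/(1 + 0.6) = 165.4, so 166. Conversely, 166 × 1.6/2.2 = 120.7 pairwise events, with power 80.1%. The figure reproduces. The protocol's sample-size text prints 0.69 with the same 166 events, whereas its synopsis and SAP 2.3 give 0.60. Only 0.60 reproduces 166, so it is used here.

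**Step 2: chance of a split result when nothing differs.** With d events in a level, power = Φ(|ln 0.60| × √d / 2 − 1.96). With powers a and b in the two levels, P(exactly one significant) = a(1 − b) + b(1 − a).

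| Factor | Events | Power | Exactly one p<0.05 |
|---|---|---|---|
| Creatinine clearance ≤50 / >50 | 24 / 97 | 24% / 71% | 61% |
| Antiplatelet yes / no | 29 / 92 | 28% / 69% | 58% |
| North America / outside | 31 / 89 | 30% / 67% | 57% |
| Female / male | 53 / 68 | 46% / 56% | 50% |

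For creatinine clearance: 0.240 × 0.291 + 0.709 × 0.760 = 0.61.

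Sensitivity: with the printed 0.69 in every level, pairwise events are 166 × 1.69/2.38 = 117.9, and the same formulas give 46% (creatinine clearance) to 42% (sex).

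**Step 3: what an interaction test does.** In 1,500 simulated two-arm trials per setting (800 patients, 117-120 events on average, constant hazard ratio 0.60, randomization stratified on both factors), a treatment-by-subgroup term rejected in 4.5-4.9% of trials. Among trials with a split result it rejected in 7-9%.

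**Step 4: limits of that test.** SE of the log ratio of hazard ratios = √(4/d₁ + 4/d₂), which is 0.455 for creatinine clearance and 0.367 for sex. Power for a ratio of 1.67 (0.60 against 1.00) is Φ(0.511/SE − 1.96), or 20% and 29%. The ratio detectable with 80% power is exp(2.80 × SE), or 3.6 and 2.8. If the tests were independent, the chance of at least one false positive would be 1 − 0.95⁷ = 30% for one dose and 1 − 0.95¹⁴ = 51% for both. The doses share a control arm, so these are upper guides.

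**Step 5: effect of dropping the randomization factors.** The documents do not give their prognostic strength, so the simulation assumed a hazard ratio of 1.5 or 2.0 for each. Omitting them moved the mean subgroup log hazard ratio by 0.003-0.010. The trial-to-trial SD of the difference was 0.02-0.08, against subgroup SEs of 0.22-0.39. The split-result rate was 54.6-57.7% without them and 54.5-57.3% with them (26/74 split), and 50.4-52.0% against 51.2-51.9% (44/56 split).

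**The case against.** The strongest objection is that Addendum 2.7 promises only hazard ratios with CIs, claims no effect modification and sets no decision rule. A careful reader can compare two intervals and approximate heterogeneity, and the p-values enter only by cross-reference to 6.6.1. This is fair as far as it goes. But readers will still see which intervals cross 1, and leaving the comparison to the eye gives it neither an estimate nor an error rate.

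A second objection is that the interaction test may be specified out of sight. SAP 6.1 defers figure formats to separate shells, and SAP 6.6.4 is redacted. Hence the claim is limited to the visible text, although 2.7 refers to 6.6.1 for the method of these subgroup analyses and not to 6.6.4.

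A third is that the interaction test is weak and, over 14 tests, prone to false positives. Both are true and should be stated with the results. Neither makes the within-level comparison a better guide.

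A reader might also infer from "with the exception that the stratification factors are not included as adjusting factors" that chance imbalance in the two factors distorts the subgroup hazard ratios and produces spurious differences. The documents do not support that. Treatment stays randomized within every subgroup, the shift is small against the standard error, and restoring the factors leaves the split-result rate almost unchanged (step 5). In the creatinine clearance and antiplatelet subgroups, one of the two factors is constant anyway. Protocol 3.2 says only that the factors may influence bleeding risk.

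**Conclusion.** The concern holds for the missing interaction. Under a constant hazard ratio of 0.60, a result significant in one level and not the other is expected in about 50% to 61% of trials for the two-level factors whose split the documents give. The within-level results therefore cannot establish that the effect differs.

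These figures are the chance of a split result given a constant effect, not the chance that a split result is misleading. They rest on the planned event count, events proportional to prevalence, and the design hazard ratio. They would differ if the trial ended with another event count or effect size. They do not cover three-level age, or race and weight, whose splits are not given.

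Omitting the randomization factors is an unexplained departure from the 6.6.1 model. It matters slightly for consistency and precision and is not a source of false effect modification. The primary and secondary analyses are unaffected.

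**What to change.** In Addendum 2.7, for each factor and dose, fit one Cox model with treatment, subgroup and treatment-by-subgroup terms (2 degrees of freedom per dose for age). Report the interaction estimate with its CI and p-value alongside the forest plot. Label the subgroup results post hoc, exploratory and unadjusted for multiplicity. State that interaction power is low (about 20-29% for a ratio of hazard ratios of 1.67) and that 14 tests carry up to about a 51% chance of at least one false positive if independent.

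As a minor point, keep the two randomization factors as covariates, omitting the one that defines the subgroup. Where cells are sparse, show that model as a sensitivity check instead. Say also whether the subgroup log-rank test is stratified.

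The cost is a few lines of addendum text and some extra code. No new data are needed.
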